4.3 Laboratory Data

Raw laboratory variables (including baseline data) will be presented by treatment group at each determination (H0, H2, H6 and D2) and contingency tables will also be displayed at the same periods.

Descriptive statistics will be presented graphically by visit according to treatment group for a selection of haematological, biochemistry and coagulation test parameters:

- Haematology: Haemoglobin (g/dL), Red cells (count/L), Hematocrit (%), Leucocytes (/mm³) and Platelets (10⁹/L);

Biochemistry: Urea (mmol/L) and Creatinin (µmol/L);

- Coagulation tests: Fibrinogen (g/L), Prothrombin (%), Quick's time (sec), Activated Thromboplastin Time Ratio and D-Dimer. The activated thromboplastin time ratio will be computed as the ratio between activated thromboplastin time "patient" (sec) and activated thromboplastin time "control" (sec).
- Factor II, Factor V and Fibrin monomer

The change from baseline for each laboratory parameter will be analysed at D2 by t test for comparing treatment groups.

4.4 Vital signs

Vital sign parameters will be described at inclusion visit, H2, H6, discharge from the obstetrics room, D2, intensive care unit discharge (if applicable) and hospital discharge :

- Systolic blood pressure (mmHg) at each visit and minimal value since last visit
- Diastolic blood pressure (mmHg) at each visit and minimal value since last visit
- Heart rate (beats/min) at each visit and minimal value since last visit

4.5 Physical examination

Physical examination will be described at inclusion and at hospital discharge.

5. TABLES, FIGURES AND GRAPHS

5.1 General Remarks about Tables

This section lists all tables and figures in the order in which they are expected to appear in the statistical report.

Table templates may be adapted as needed at the time the statistical analyses are performed.

5.2 List of tables

Table	Number	Title
HEADING	14.1	STUDY PATIENTS
HEADING	14.1.1	DISPOSITION OF PATIENTS
Table	14.1.1.1	Recruitment of Patients - ITT Set
Table	14.1.1.2	Overall Patient Disposition - ITT Set
Table	14.1.1.3	Disposition by Visit, withdrawal and reasons - ITT Set
HEADING	14.1.2	PROTOCOL DEVIATIONS
Table	14.1.2.1	Number (%) of Patients by Reason for Exclusion from the Per Protocol Set (Major Deviations) - ITT Set
Table	14.1.2.2	Number (%) of Patients by Protocol Deviation Other than Major Protocol Deviations (Minor Deviations) - ITT Set
HEADING	14.1.3	DEFINITION OF ANALYSIS SETS
Table	14.1.3.1	Number (%) of Patients in Each Analysis Population / ITT Set
HEADING	14.1.4	DEMOGRAPHIC AND BASELINE CHARACTERISTICS ^a
Table	14.1.4.1	Demographic Data by Treatment Group - ITT Set
Table	14.1.4.2	Physical Examination by Treatment Group – ITT Set
Table	14.1.4.3	Pregnancy Parameters by Treatment Group - ITT Set
Table	14.1.4.4	Obstetrical History by Treatment Group - ITT Set
Table	14.1.4.5	Surgical and Medical History by Treatment Group - ITT Set
Table	14.1.4.6	Surgical and Medical History by Treatment Group, System Organ Class and Preferred Term - ITT Set
Table	14.1.4.7	Delivery Parameters by Treatment Group - ITT Set
Table	14.1.4.8	Post-Partum Haemorrhage Parameters at Inclusion by Treatment Group - ITT Set
Table	14.1.4.9	Prostaglandin infusion by Treatment Group – ITT Set
Table	14.1.4.10	Previous Treatments - Intravenous Fluids Before Study Treatment Administration by Treatment Group - ITT Set
Table	14.1.4.11	Previous Treatments - Tranexamic Acid Before Study Treatment Administration by Treatment Group - ITT Set
Table	14.1.4.12	Other Previous Treatments According to ATC and Preferred Name by Treatment Group - ITT Set
HEADING	14.1.5	INVESTIGATIONAL PRODUCT (IMP) AND CONCOMITANT TREATMENTS

^a Demographic and baseline characteristics for ITT and PP set will be presented in appendix in the same order they are mentioned in the list of table.

Table	Number	Title
Table	14.1.5.1	Number and percentage of patients exposed by Treatment Group - ITT Set
Table	14.1.5.2	Study Treatment Administration by Treatment Group - ITT Set
Table	14.1.5.3	Duration of exposure by Treatment Group - ITT Set
Table	14.1.5.4	Compliance by Treatment Group – ITT Set
Table	14.1.5.5	Number and percentage of patients receiving receiving at least one transfusion of RBCs – ITT Set
Table	14.1.5.6	Number and percentage of patients receiving FFP and platelet units – ITT Set
Table	14.1.5.7	Number and percentage of patients receiving fibrinogen concentrate as rescue therapy – ITT Set
Table	14.1.5.8	Number and percentage of patients with tranexamic acid administration – ITT Set
Table	14.1.5.9	Chronological order of administration of concomitant treatments – ITT Set
Table	14.1.5.10	Concomitant Treatments According to to Anatomical Therapeutic Chemical Classification and Preferred Name by Treatment Group – ITT Set
HEADING	14.2	EFFICACY ANALYSIS
HEADING	14.2.1	PRIMARY EFFICACY ANALYSIS OF THE PRIMARY ENDPOINT
Table	14.2.1.1	Primary Efficacy Analysis of the Primary Endpoint - Logistic regression model adjusting for treatment, centre and baseline fibrinogen – ITT Set without imputation of missing data
Table	14.2.1.2	Validity of the Primary Efficacy Analysis – ITT Set without of missing data
HEADING	14.2.2	SECONDARY MAJOR ANALYSES OF THE PRIMARY ENDPOINT AND SENSITIVITY ANALYSES
Table	14.2.2.1	Secondary Major Efficacy Analysis of the Primary Endpoint assuming MAR missingness mechanism – ITT Set
Table	14.2.2.2	FCS multivariate imputation estimations – ITT Set
Table	14.2.2.3	Sensitivity analysis Efficacy Analysis of the Primary Endpoint assuming missingness mechanism as failure – ITT Set
Table	14.2.2.4	Per protocol analyses of the primary efficacy endpoint – PP Set
HEADING	14.2.3	OTHER EFFICACY ANALYSES OF THE PRIMARY ENDPOINT
Table	14.2.3.1	Logistic regression model adjusting for treatment, centre and continuous baseline fibrinogen – ITT Set without imputation of missing data
Table	14.2.3.2	Logistic regression model adjusting for treatment, categorized fibrinogen at baseline, treatment * categorised fibrinogen and centre * treatment interactions – ITT Set without imputation of missing data
Heading	14.2.4	INDIVIDUAL COMPONENT ANALYSES OF THE PRIMARY ENDPOINT
Table	14.2.4.1	Analyses of administration of at least 2 units of RBCs from H0 to D2 - ITT SET
Table	14.2.4.2	Analyses of the percentage of patients losing at least 4g/dL of Hb from H0 to D2 - ITT SET
HEADING	14.2.5	SUBGROUP ANALYSES ^b
Table	14.2.5.1	Analyses of failure rate by treatment group and level of categorized prognostic factors – ITT Set without imputation of missing data
Table	14.2.5.2	Univariate logistic regression of the influence of prognostic factors – ITT Set without imputation of missing data
Table	14.2.5.3	Stepwise logistic regression of the influence of prognostic factors and interactions – ITT Set without imputation of missing data
HEADING	14.2.6	SECONDARY EFFICACY ANALYSES ^b

^b All secondary efficacy tables will be duplicated to the description of PP set.

Table	Number	Title
Heading	14.2.6.1	Analyses of the key secondary efficacy variables
Table	14.2.6.1.1	Calculated volume of total blood loss, 48 hours following IMP administration – ITT set
Table	14.2.6.1.2	Percentage of patients requiring any need for rescue procedure – ITT set
Table	14.2.6.1.3	Percentage of patients requiring the use of intrauterine balloon within 48 hours following the IMP administration – ITT set
Heading	14.2.6.2	Analyses of the other secondary efficacy variables
Heading	14.2.6.2.1	Change from baseline in plasma fibrinogen level (g/L) at H2, H6 and D2 compared between treatment groups
Table	14.2.6.2.1.1	Descriptive statistics of plasma fibrinogen parameter at each time - ITT set
Table	14.2.6.2.1.2	Analyses of change from baseline – Student t test - ITT set
Heading	14.2.6.2.2	Change from baseline for Hb, Ht and RBCs parameters at H2, H6 and D2 compared between treatment groups
Table	14.2.6.2.2.1	Descriptive statistics of Hb, Ht and RBCs parameters at each time - ITT set
Table	14.2.6.2.2.2	Analyses of change from baseline – Student t test - ITT set
Heading	14.2.6.2.3	Analyses of the evolution of haemorrhage
Table	14.2.6.2.3.1	Analyses of the evolution of haemorrhage by treatment group - ITT set
Table	14.2.6.2.3.2	Analyses of the number of units of transfused blood units – ITT set
Table	14.2.6.2.3.3	Analyses of the duration of haemorrhage by treatment group - ITT set
Heading	14.2.6.2.4	Haemostatic intervention and maternal morbidity
Table	14.2.5.5.1	Description of haemostatic interventions by treatment group - ITT set
Table	14.2.5.5.2	Analysis of length of stay in the obstetrics room, duration of hospitalization and number of days with assisted ventilation by treatment group – ITT set
Table	14.2.5.5.3	Analysis of the number of days in resuscitation and/or intensive care and/or PICU and/or continuous care units – Student t test - ITT set
Table	14.2.5.5.4	Descriptive statistics of maximal SOFA score by treatment group - ITT set
Heading	14.2.6.2.5	Laboratory parameters (Haematology, Biochemistry and coagulation tests)
Table	14.2.6.2.5.1	Descriptive statistics of haematology parameters at each time
Figure	1	Graphical representation of haemoglobin (g/dL) parameter by visit and by group (Inclusion, Hour 2, Hour 6 and Day 2) and change from baseline - ITT set
Figure	2	Graphical representation of red cells (count/L) parameter by visit and by group (Inclusion, Hour 2, Hour 6 and Day 2) and change from baseline - ITT set
Figure	3	Graphical representation of hematocrit (%) parameter by visit and by group (Inclusion, Hour 2, Hour 6 and Day 2) and change from baseline - ITT set
Figure	4	Graphical representation of Leucocytes (/mm ³) parameter by visit and by group (Inclusion, Hour 2, Hour 6 and Day 2) and change from baseline - ITT set
Figure	5	Graphical representation of Platelets (10 ⁹ /L) parameter by visit and by group (Inclusion, Hour 2, Hour 6 and Day 2) and change from baseline - ITT set
Table	14.2.6.2.5.2	Descriptive statistics of biochemistry parameters at each time
Figure	6	Graphical representation of Urea (mmol/L) parameter by visit and by group (Inclusion, Hour 2, Hour 6 and Day 2) and change from baseline - ITT set
Figure	7	Graphical representation of Creatinin (µmol/L) parameter by visit and by group (Inclusion, Hour 2, Hour 6 and Day 2) and change from baseline - ITT set

Table	Number	Title
Table	14.2.6.2.5.3	Descriptive statistics of coagulation parameters at each time - ITT SET
Figure	8	Graphical representation of Prothrombin (%) parameter by visit and by group (Inclusion, Hour 2, Hour 6 and Day 2) and change from baseline - ITT set
Figure	9	Graphical representation of Activated Thromboplastin Time Ratio parameter by visit and by group (Inclusion, Hour 2, Hour 6 and Day 2) and change from baseline - ITT set
Figure	10	Graphical representation of D-Dimer parameter by visit and by group (Inclusion, Hour 2, Hour 6 and Day 2) and change from baseline - ITT set
Figure	11	Graphical representation of factor II parameter by visit and by group (Inclusion, Hour 2, Hour 6 and Day 2) and change from baseline - ITT set
Figure	12	Graphical representation of factor V parameter by visit and by group (Inclusion, Hour 2, Hour 6 and Day 2) and change from baseline - ITT set
Figure	13	Graphical representation of fibrin monomer parameter by visit and by group (Inclusion, Hour 2, Hour 6 and Day 2) and change from baseline – ITT set
HEADING	14.3	SAFETY ANALYSIS
Heading	14.3.1	Description of vital sign parameters at each visit
Table	14.3.1.1	Systolic and diastolic blood pressure at each visit – SS
Table	14.3.1.2	Heart rate at each visit – SS
Table	14.3.1.3	Peripheral oxygen saturation – SS
Heading	14.3.2	Physical examination at hospital discharge
Table	14.3.2.1	Physical examination at hospital discharge – SS
HEADING	14.3.3	ADVERSE EVENTS
Table	14.3.3.1	Overall Summary of Adverse Events by treatment group – SS
Table	14.3.3.2	Adverse Event by Primary System Organ Class, Preferred Term by treatment group – SS
Table	14.3.3.3	Adverse Event Related to Treatment by Primary System Organ Class, Preferred Term by treatment group – SS
Table	14.3.3.4	Adverse Event by Primary System Organ Class, Preferred Term, Severity by treatment group- SS
Table	14.3.3.5	Serious Adverse event by Primary System Organ Class, Preferred Term by treatment group- SS
HEADING	14.3.4	TREATMENT EMERGENT ADVERSE EVENTS
Table	14.3.4.1	Overall Summary of Treatment Emergent Adverse Events by treatment group – SS
Table	14.3.4.2	Treatment Emergent Adverse Event by Primary System Organ Class, Preferred Term by treatment group – SS
Table	14.3.4.3	Treatment Emergent Adverse Event Related to Treatment by Primary System Organ Class, Preferred Term by treatment group – SS
Table	14.3.4.4	Treatment Emergent Adverse Event by Primary System Organ Class, Preferred Term, Severity by treatment group- SS
Table	14.3.4.5	Serious Treatment Emergent Adverse event by Primary System Organ Class, Preferred Term by treatment group- SS
HEADING	14.3.5	INDIVIDUAL DATA LISTING OF ADVERSE EVENTS
Listing	14.3.5.1	Listing of Aes related to treatment – SS
Listing	14.3.5.2	Listing of Aes leading to treatment discontinuation – SS
Listing	14.3.5.3	Listing of SAEs – SS

Table	Number	Title
Listing	14.3.5.4	Listing of deaths – SS

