12.11. Safety Analysis

Analyses of safety endpoints will be conducted in the safety set. Missing data will not be replaced.

With respect to AEs, all AEs occurring during the treatment period will be classified using the Lowest Level Term (LLT), Preferred Terms (PT) and System Organ Class (SOC). The duration of the AE and the duration between the last dose of IMP and onset of the adverse event will be calculated.

The number of patients with at least one AE will be tabulated by treatment group, SOC, PT and LLT. Patients with SAEs, IMP-related AEs and other significant AEs will be tabulated by treatment group, SOC, PT and LLT.

The number of AEs will be tabulated by treatment group, SOC, PT and LLT.

All SAEs, IMP-related AEs and other significant AEs will be listed by treatment group, SOC, PT and LLT.

The standard dictionary for coding events will be the MedDRA (version 16.0).

AEs reported before the start of IMP infusion will only be listed with individual patient's AE data collected, if applicable.

Raw laboratory variables (including baseline data) will be presented by treatment group at each determination (H0, H6 and D2) and shift tables will also be displayed at the same periods. Determinations at other sampling times will be listed except if other specific times are defined in the SAP.

Arterial and venous thromboembolic events over the study period will be compared between treatment groups by chi-square.

No statistical tests will be performed on other variables except if it is needed to explore any AE with possible clinical significance.

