Secondary analyses	"[...] all secondary efficacy variables will be compared between the 2groups using chi-square for categorical data and using t test for continuous quantitative data or other appropriate	SAP: "The change in plasma fibrinogen level, Hb and Ht will be analysed at H2, H6 and D2 following IMP administration with a Mixed Model for Repeated Measures (MMRM) comparing the Clottafact [®] group and placebo

	tests.”	group.”
Multiplicity	None	
SAP: “No multiplicity adjustment is necessary for the primary analysis as there is only one primary criterion and two arms compared. The 2-sided nominal alpha level of significance is set to 5%. Results for the two components of the composite primary endpoint will be individually examined without statistical hypothesis testing.
 
Secondary efficacy parameters will be tested for superiority at the 5% level of the Clotfact[®] arm, compared to the placebo arm. Secondary efficacy variables will be examined and may contribute to supportive information to the effectiveness. We distinguish two types of secondary endpoints: (1) Key secondary endpoints are defined as highly clinically relevant endpoints. Statistical methods for addressing multiplicity issues will be used to test sequentially key secondary endpoints (ie. Hochberg procedure); (2) other secondary endpoints will be analysed in an exploratory purpose.”

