- 1- Change in plasma fibrinogen level (g/L) between H2 and H0
- 2- Change in plasma fibrinogen level (g/L) between H6 and H0
- 3- Change in plasma fibrinogen level (g/L) between D2 and H0
- 4- The same changes will be calculated for Hb, Ht and RBCs
- 5- Duration of haemorrhage (hours): end time of haemorrhage – start time of haemorrhage

- 6- Duration in the obstetrics room (from arrival hour in obstetrics room to delivery hour)
- 7- Duration of hospitalization (from arrival date in obstetrics room to hospital discharge date)
- 8- Number of days in resuscitation and/or intensive care and/or PICU and/or continuous care units (admission date and discharge date)
- 9- Number of days with assisted ventilation

3.3.6.3.2 *Analyses of secondary efficacy variables*

3.3.6.3.2.1 Analyses of key secondary variables

The analyses of key secondary variables will be tested with the Hochberg step-up method:

- 1- Calculated/estimated volume of total blood loss, 48 hours following IMP administration

The estimated/calculated volume of total blood loss 48 hour after IMP administration will be compared between the Clottafact[®] group and placebo group by a t test or non parametric test.

- 2- Percentage of patients requiring any need for rescue procedure

The percentage of patients requiring any need for rescue procedure within 48 hours following IMP administration will be calculated and chi-square or Fisher exact tests will be used to compare between the Clottafact[®] group and placebo group.

- 3- Percentage of patients requiring the use of intrauterine balloon within 48 hours following IMP administration

The percentage of patients requiring the use of intrauterine balloon within 48 hours following the administration will be calculated and chi-square or Fisher exact tests will be used to compare between the Clottafact[®] group and placebo group.

3.3.6.3.2.2 Other analyses of secondary variables

Other secondary endpoints will be analysed in an exploratory purpose.

3.3.6.3.2.2.1 Analyses of the change from baseline in plasma fibrinogen level, Hb and Ht

The evolution in plasma fibrinogen level, Hb and Ht will be analysed at H2, H6 and D2 following IMP administration with a Mixed Model of Repeated Measurements comparing the Clottafact[®] group and placebo group.

3.3.6.3.2.2.2 Analyses of the evolution of haemorrhage

3.3.6.3.2.2.2.1 Analyses of haemoglobin level

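### The SAP names a repeated-measures model for the fibrinogen, Hb and Ht changes but tabulates only Student t tests, adds unlogged D2 laboratory tests, and specifies no baseline covariate in any of them

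*SAP*

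**What the plan says.** Four places in the SAP and two in the protocol bear on these analyses.

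- **SAP 3.3.6.3.2.2.1:** plasma fibrinogen, Hb and Ht "will be analysed at H2, H6 and D2 following IMP administration with a Mixed Model of Repeated Measurements". The change log in SAP 2.2 records the same model as a departure from the protocol's chi-square and t tests.
- **SAP 5.2:** Tables 14.2.6.2.1.2 (fibrinogen) and 14.2.6.2.2.2 (Hb, Ht, RBC) both carry the title "Analyses of change from baseline – Student t test - ITT set". The second stands under the heading "Change from baseline for Hb, Ht and RBCs parameters at H2, H6 and D2 compared between treatment groups". No listed table is titled for a mixed model, and SAP 7 gives no code for one.
- **SAP 4.3 (safety):** "The change from baseline for each laboratory parameter will be analysed at D2 by t test for comparing treatment groups". Its list opens with "Haematology: Haemoglobin (g/dL), Red cells (count/L), Hematocrit" and also includes fibrinogen.
- **SAP 3.3.6.3.2.2:** these endpoints are exploratory.
- **Protocol 12.10.1.3.2 (efficacy):** changes in laboratory parameters are compared by t test.
- **Protocol 12.11 (safety):** thromboembolic events are compared by chi-square. Beyond that, "No statistical tests will be performed on other variables except if it is needed to explore any AE with possible clinical significance".

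**The concern.** The biological effect of fibrinogen is a stated secondary objective, and the change in plasma fibrinogen is its named endpoint. For that endpoint, and for Hb and Ht, the SAP describes one method in the text, tabulates another, and tests the D2 change again under safety. No section says which result counts. SAP 5.1 lets table templates be adapted when the analyses are run, so the choice between methods could be made after treatment codes are known.

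Two further gaps follow. The D2 tests in SAP 4.3 extend safety testing beyond the protocol without being declared as a change. And no version of the analysis uses the baseline value as a covariate, although it is measured at inclusion (protocol 8.2.1, blood sampling 1).

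**Working it through.** The plan states no figure for these endpoints, so there is none to reproduce; its sample size concerns the primary endpoint only.

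**1. The methods side by side**

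| Change in | SAP 3.3.6.3.2.2.1 | SAP 5.2 tables | SAP 4.3 |
|---|---|---|---|
| Fibrinogen | Mixed model: H2, H6, D2 | t test: H2, H6, D2 | t test: D2 |
| Hb, Ht | Mixed model: H2, H6, D2 | t test: H2, H6, D2 | t test: D2 |
| RBC count | Not named | t test: H2, H6, D2 | t test: D2 |
| Other laboratory parameters | Not named | Descriptive only | t test: D2 |

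SAP 4.3 lists 15 parameters: 5 haematology, 2 biochemistry, 5 coagulation, and factor II, factor V and fibrin monomer. Taking out fibrinogen, Hb, Ht and RBC leaves 15 − 4 = 11.

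**2. How many different p-values**

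The tabulated t test uses the ITT set and the SAP 4.3 test uses the safety set. By SAP 3.1.2 these coincide if there are no allocation errors, and the two D2 t tests then agree. That leaves two distinct p-values for D2 fibrinogen, Hb and Ht (mixed model and t test), and one for RBC.

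The mixed model and the t test need not differ. With complete data, unstructured covariance, a treatment-by-visit term and no baseline term, the model's D2 contrast is the same difference in mean changes. They separate if:

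- D2 samples are missing, because the model also uses H2 and H6 while the t test uses only women with a D2 sample (protocol 8.2.5 foresees transfers by then);
- the covariance is constrained;
- treatment by visit is left out; or
- baseline is added.

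The SAP fixes none of the three modelling choices.

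**3. Authority for the D2 safety tests**

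Protocol 12.11 allows tests on thromboembolic events and tests needed to explore an adverse event of possible clinical significance. A routine D2 test on every parameter is neither. SAP 2.2 has no row for it. SAP 5.2 has no output for it either: the tables numbered 14.2.6.2.5 are descriptive, and 14.3 has no laboratory table. Protocol 12.8.4 and SAP 3.3.5.4 class laboratory data as safety criteria except those defined as efficacy variables, so testing fibrinogen, Hb, Ht and RBC under SAP 4.3 also crosses the plan's own division.

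**4. What baseline adjustment is worth**

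Let r be the baseline to follow-up correlation and assume the same SD, σ, at both times. The documents give neither, so r is shown as a range.

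- Change score: variance 2(1 − r)σ².
- Baseline-adjusted: variance (1 − r²)σ².
- Ratio, adjusted to change: (1 − r²) / [2(1 − r)] = (1 + r)/2.

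| r (assumed) | Change (σ²) | Adjusted (σ²) | Ratio | Reduction |
|---|---|---|---|---|
| 0.3 | 1.40 | 0.91 | 0.65 | 35% |
| 0.5 | 1.00 | 0.75 | 0.75 | 25% |
| 0.7 | 0.60 | 0.51 | 0.85 | 15% |
| 0.9 | 0.20 | 0.19 | 0.95 | 5% |

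For scale, SAP 1.11 gives 448 patients less 1.55%: 448 × 0.9845 / 2 ≈ 220 per arm. For an assumed difference of 0.25 SD, power of the change-score t test against the adjusted analysis is 60.1% against 78.5% (r = 0.3), 74.6% against 85.7% (r = 0.5) and 92.3% against 95.7% (r = 0.7).

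In 10,000 simulated trials under no effect, the change-score t test rejected in 5.2%, 4.9% and 4.9% at the same three correlations. It holds its level; the loss is one of precision.

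**The case against.** The best defence is that this is editorial. The methods text and the change log agree with each other, and the protocol's original method was the t test, so the two table titles look like leftovers. The endpoints are exploratory and outside the Hochberg family. That limits the consequences. It does not supply a rule of precedence, and it does not explain the tests in SAP 4.3.

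Several stronger readings are tempting and are not supported:

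- **That the t tests ignore baseline.** They are made on change from baseline, so baseline is subtracted. Only covariate adjustment is absent, which costs precision and not validity.
- **That the tabulated method is less precise than the adopted one.** The SAP's mixed model names no baseline covariate either. The gain shown belongs to adding baseline, not to the model as written.
- **That chance findings in the safety laboratory data are likely.** Fifteen independent tests at 5% would give 1 − 0.95^15 = 54% for at least one false positive. That is an upper illustration: Hb, Ht and red cells move together, as do prothrombin and Quick's time, and fibrinogen is the infused product.
- **That RBC count shares the model conflict.** It is not in the mixed-model text; its only duplication is between two t tests.
- **That SAP 4.2 contradicts SAP 4.3 outright.** SAP 4.2 says no other variables are tested, but it stands under adverse events and may cover only those. The firm limit is protocol 12.11.

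**Conclusion.** The inconsistency holds. For fibrinogen, Hb and Ht the SAP adopts a repeated-measures model, tabulates only t tests on change, and retests the D2 change under safety, with no precedence among them. The same D2 change can therefore carry two different p-values, or a third if allocation errors make the safety and ITT sets differ. The D2 tests in SAP 4.3 exceed protocol 12.11 and are undeclared in SAP 2.2.

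The missing baseline covariate is a separate loss, common to all versions as written. Its size depends wholly on the assumed correlation and on equal variances at the two times.

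The primary and key secondary conclusions are untouched. The point still deserves correction, because a stated secondary objective should have one defined analysis, chosen before treatment codes are known.

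**What to change.** - **One analysis.** Make the repeated-measures model the single analysis of change in fibrinogen, Hb and Ht. Specify treatment, visit, treatment by visit, baseline value (by visit) and the covariance structure.
- **Tables.** Retitle Tables 14.2.6.2.1.2 and 14.2.6.2.2.2 to that model.
- **RBC count.** State its method; the same model is suitable.
- **SAP 4.3.** Remove fibrinogen, Hb, Ht and RBC from the D2 t tests. For the remaining 11 parameters, either present them descriptively, in line with protocol 12.11, or record the added tests as a change in SAP 2.2.

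The cost is SAP wording, table titles and the model code that SAP 7 lacks. No new data are needed, since the baseline values come from blood sampling 1.
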